5.3 Patient Withdrawal Criteria

5.3.1 Discontinuation from Treatment

The term "treatment interruption" refers to a patient stopping the study drug during the course of the study, but then re-starting it at a later time in the study (see Section 6.1). The reason for dosing interruption will be collected on the patient's source data and eCRF.

The term "treatment discontinuation" refers to a patient's withdrawal from the study treatment phase. The reason for discontinuation from treatment will be collected on the patient's source data and eCRF.

Treatment discontinuation should be discussed where possible with the Sponsor before the patient stops treatment with the study medication, and the Study Monitor should be notified before treatment discontinuation.

Patients may be discontinued from treatment in case of:

- Disease progression according to RECIST v1.1. However, patients are allowed to continue on treatment based on medical judgement.
- Deterioration in the general health status of the patient without evidence of disease progression according to RECIST v1.1.
- Unacceptable toxicity or AE.
- Pregnancy (Section 5.3.4).
- Patient withdraws consent to continue treatment.

Patients who discontinue study medication for any reason should not be considered as discontinued from study (Section 5.3.2); these patients should be requested to attend the EoT visit, the 30-day Safety Follow-up visit and the Long-term Follow-up visits as outlined in the Study Schedule (Section 1.1), unless consent to participate in the study and consent to be followed for OS is also withdrawn (Section 5.3.3).

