6.1.1 Dosing and Administration

Patients will be randomized to one of the following two treatment regimens:

Balixafortide + eribulin treatment arm

Balixafortide will be administered on Days 1–3 and Days 8–10 and eribulin will be administered on Days 2 and 9 of each 21-day cycle.

[figure not shown]
Cycle Scheme:

Eribulin monotherapy treatment arm

Eribulin will be administered on Days 2 and 9 of each 21-day cycle.

Cycle Scheme:

Balixafortide will be administered, at a dose of 5.5 mg/kg, IV over a minimum of 2 hours ±10 minutes; however, the infusion time of balixafortide can be increased to a maximum of 3 hours at the discretion of the treating physician, for reasons of patient tolerability (i.e. to manage IRRs).

Protocol No.: POL6326-009

Version 3.0

Eribulin should be administered IV at a dose of 1.4 mg/m² over 2 to 5 minutes on Days 2 and 9 of each 21-day cycle; **note:** this dose is expressed as the salt, eribulin mesylate; however, in some countries this dose is expressed as the base, equivalent to eribulin 1.23 mg/m². In the balixafortide + eribulin treatment arm, eribulin will be administered within 45 minutes after the end of the balixafortide infusion. The eribulin dose should be modified in patients with hepatic and/or renal impairment as described in the regulatory label for eribulin in the country where the patient is being treated or as described in Table 4 (Section 6.1.2) for other countries.

Crossover will not be allowed at any time after randomization.

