6.1.2 Dose Modifications (including delays and interruptions)

Balixafortide

Balixafortide dosing may be modified for reasons of patient tolerability as described below. Patients are to be instructed to notify Investigators at the first occurrence of any adverse sign or symptom.

Dosing modifications for balixafortide may occur in 2 ways:

- Within a cycle: dosing interruption during a given treatment cycle until there is adequate recovery to Grade 1 or lower.
- Between cycles: administration of the next cycle may be delayed due to persistent toxicity.

Based on currently available data, there are no dose reductions recommended for balixafortide. Investigators should discuss with the Sponsor in a timely manner, any balixafortide dose reduction they feel warranted for that patient due to AEs and possible resumption of balixafortide at the full dose.

In the rare event that patients are discontinued from balixafortide treatment due to treatment-related toxicity, patients should attend the EoT Visit, the 30-day Safety Follow-up visit, and the Long-term Follow-up visits.

Eribulin

The recommended dose reductions for eribulin are presented in Table 4 and based on the US label (43) as reference. In countries where eribulin is approved, guidance on dose modification provided in the local, currently approved eribulin label may be followed. The eribulin dose should not be escalated after it has been reduced.

Sponsor Logo/Name: Polyphor Ltd Date: 15 July 2019 Protocol No.: POL6326-009

Version 3.0

Table 4 Recommended dose reductions for eribulin

Event description	Recommended dose						
	Expressed as salt (eribulin mesylate)	Expressed as base (eribulin)					
Mild hepatic impairment (Child-Pugh A)	1.1 mg/m ²	0.97 mg/m ²					
Moderate hepatic impairment (Child Pugh B)	0.7 mg/m ²	0.62 mg/m ²					
Moderate or severe renal impairment (CrCl 15–49 mL/min)	1.1 mg/m ²	0.97 mg/m ²					
Permanently reduce the 1.4 mg/m² of eribulin mesylate dose (equivalent to 1.23 mg/m² eribulin base) for any of the following							
ANC <500/mm ³ for >7 days	1.1 mg/m ²	0.97 mg/m ²					
ANC <1,000/mm ³ with fever or infection	1.1 mg/m ²	0.97 mg/m ²					
Platelets <25,000/mm ³	1.1 mg/m ²	0.97 mg/m ²					
Platelets <50,000/mm ³ requiring transfusion	1.1 mg/m ²	0.97 mg/m ²					
Non-hematological Grade 3 or 4 toxicities	1.1 mg/m ²	0.97 mg/m ²					
Omission or delay of Day 9 eribulin dose in previous cycle for toxicity	1.1 mg/m ²	0.97 mg/m ²					

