6.1.2.1 Dosing Delays or Interruptions

Patients will start study medication within 3 days from randomization as outlined in the Study Schedule (Section 1.1). Subsequent cycles of treatment should be started within 3 days of completing the previous cycle. Any delays beyond this that are being considered to the beginning of a cycle for logistical or scheduling reasons should be discussed with the Sponsor on a case by case basis.

If study medication during a cycle is delayed for <14 days (counted from the beginning of dosing in that cycle), then treatment can be resumed during that cycle. In these circumstances, the total duration of a cycle could potentially be extended up to 27 days.

Protocol No.: POL6326-009

Version 3.0

If study medication during a cycle is delayed for ≥14 days (counted from the beginning of dosing in that cycle), then treatment for that cycle cannot be resumed. Instead, the next cycle will be initiated as planned. If the next cycle cannot be initiated as planned, the patient should be discontinued from treatment unless discussed and agreed otherwise with the Sponsor.

The doses of balixafortide on Days 1, 2 and 3 are interdependent with the eribulin dose on Day 2. Similarly, the doses of balixafortide on Days 8, 9 and 10 are interdependent with the eribulin dose on Day 9. Therefore, if an eribulin dose is delayed by a few days during a cycle, then the adjunctive balixafortide doses must also be delayed accordingly during that cycle. Although delays of <14 days (counted from the beginning of dosing in that cycle) may change the days on which doses are given in relation to the Schedule, the interval between doses in a cycle should remain the same as those shown in Section 6.1.1. If a dose of eribulin is omitted, the corresponding dose/s of balixafortide must also be omitted. Some examples of the circumstances that could arise are given below:

- Example 1, if eribulin is given on Day 3 instead of Day 2, then balixafortide can be given on Days 2, 3 and 4 instead of on Days 1, 2 and 3.
- Example 2, if eribulin is given on Day 12 instead of Day 9, then balixafortide can be given on Days 11, 12 and 13.
- Example 3, if eribulin is omitted on Day 9, then the balixafortide on Days 8, 9, and 10 can also be omitted.

Tumor assessments must continue to be performed according to the Study Schedule regardless of any dosing delay (Section 8.2).

Recommended Dose Delays for Eribulin

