7.6 End of Treatment Visit

Patients who discontinue treatment will attend the EoT Visit (i.e. withdrawal) as soon as possible, within 7 days after discontinuation and prior to initiation of any new anti-cancer therapy, regardless of the reason for discontinuation.

All patients:

- Patient reported health outcome QoL questionnaires (see Section 11.3).
- Targeted physical examination (see Section 9.6).
- Vital signs (resting BP, respiratory rate, pulse rate, and body temperature; see Section 9.7).
- Weight.
- ECOG performance status (see Section 9.6).
- AE reporting (see Section 9.2).
- Concomitant therapy/medications taken since the previous visit (see Section 5.4.1).
- 12-lead ECG (see Section 9.8).
- Clinical laboratory tests (hematology, chemistry, and urinalysis; see Section 9.9).
- Urine pregnancy test for women of child bearing potential (see Section 5.4.5.1).
- CT/MRI scan (see Section 8.2.2) in patients who are discontinued from study medication in the absence of PD; however, patients who have already demonstrated objective PD (according to RECIST v 1.1) do not need to have scans repeated at the EoT visit.

Sponsor Logo/Name: Polyphor Ltd Date: 15 July 2019 Protocol No.: POL6326-009

Version 3.0

version 3.0

 Blood samples for immunogenicity only for patients from the balixafortide + eribulin treatment arm (see Section 11.1).

- Document reason for treatment discontinuation.
- IWRS/IRT registration.

Patients at Selected Sites Only:

For patients at selected sites, the following additional assessments will be performed:

- Optional tumor biopsy (see Section 11.2.1).
- Blood samples for other exploratory biomarkers in patients at selected sites (see Section 11.2.2).

7.7 30-Day Safety Follow-up

The 30-day safety follow-up visit will be scheduled 30 days (and no later than 37 days) after the last dose of study drug and can be conducted over the telephone. If for any reason the safety follow-up occurs earlier than scheduled (e.g. initiation of new anticancer therapy, withdrawal of consent), the time of the visit should be documented along with the reasons for the early follow-up; the data from these visits will be evaluated separately.

All Patients:

- AE reporting (see Section 9.2).
- Concomitant therapy/medications taken since the previous visit to be recorded for patients with unresolved AEs (see Section 5.4.1).

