9.2.6.3 Infusion-Related Reactions

Acute IRRs and hypersensitivity events due to histamine release, such as rash, pruritus, erythema and flushing may occur. The majority of hypersensitivity events in the earlier studies occurred during first administration and were generally dose dependent.

All patients should be observed during the infusion of balixafortide and recommended dosage and infusion duration closely adhered to. An antihistamine kit must be kept available for immediate intervention in case of IRRs. Prophylactic use of H₁ receptor antagonists may be used for premedication at the discretion of the treating physician.

For management of IRRs:

- The balixafortide infusion should be interrupted and vital signs monitored until the IRR resolves to Grade ≤1 and then the infusion can be restarted at a slower rate.
- Treatment with antihistamines and methylprednisolone can be initiated, or other treatments can be given as necessary in line with the patient's condition and local standard of care.
- The patient can be pre-treated with antihistamines prior to the next balixafortide infusion.
- If the IRR continues, the balixafortide infusion rate can be slowed down to 3 hours and if not resolved, the Sponsor contacted.

When anaphylaxis is suspected and/or confirmed, treatment with epinephrine must be initiated immediately. In case of severe reactions, the infusion of balixafortide should be stopped immediately and treatment discontinued permanently.

AEs of IRRs and hypersensitivity must be captured on the patient's source data and AE eCRF page, along with their signs and symptoms. If dosing is interrupted, discontinued or the patient is withdrawn from the study as a result of an infusion site reaction, this must be recorded in the patient's source data and eCRF.

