3.4. Dose Adjustment/Modifications

3.4.1. Dose Modification Balixafortide

In the event of significant treatment-related toxicity, balixafortide + eribulin dosing may be modified in two ways:

- Within a cycle: dosing interruption during a given treatment cycle until there is adequate recovery;
- Between cycles: administration of the next cycle may be delayed due to persistent toxicity.

Patients that discontinue from balixafortide treatment due to treatment-related toxicity are to attend an EoT Visit within 7 days after discontinuation, the 30-day safety follow-up visit for assessments and recording of AEs and concomitant medications, and the Long-term Follow-up visits.

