9.1.5. Adverse Events Leading to Study Treatment Discontinuation

Following the AE, the investigator will record the action taken with each of the study treatments. If at least one of the drugs has an action taken equal to 'Drug Withdrawn', then the AE will be considered as leading to study treatment discontinuation. The summary table will present overall covering all treatment discontinuations, and separately for each of balixafortide and eribulin where Action Taken with respective treatment is 'Drug Withdrawn'. A summary table by CTCAE grade will also be presented.

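### Stopping balixafortide for toxicity leads to the end-of-treatment visit with no provision for eribulin alone, so a severe Day 1 reaction can leave a combination-arm patient with no study eribulin

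*Protocol*

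**What the plan says.** **Dosing order.** In the combination arm balixafortide is given on Days 1–3 and 8–10, and "eribulin will be administered on Days 2 and 9 of each 21-day cycle" (protocol 6.1.1). The first study drug such a patient receives is therefore balixafortide, a day before any eribulin. The same section bars cross-over.

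**Stopping balixafortide.** Protocol 6.1.2: "In the rare event that patients are discontinued from balixafortide treatment due to treatment-related toxicity, patients should attend the EoT Visit". The 30-day safety visit and long-term follow-up come after it. SAP 3.4.1: "Patients that discontinue from balixafortide treatment due to treatment-related toxicity are to attend an EoT Visit within 7 days after discontinuation".

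**What the end-of-treatment (EoT) visit means.** Protocol 7.6: "Patients who discontinue treatment will attend the EoT Visit (i.e. withdrawal) as soon as possible". Under protocol 5.3.1, treatment discontinuation "refers to a patient's withdrawal from the study treatment phase".

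**Infusion reactions.** Protocol 9.2.6.3: "The majority of hypersensitivity events in the earlier studies occurred during first administration". Milder reactions are managed by interrupting or slowing the infusion and with antihistamines and steroids. After a severe reaction the infusion stops at once and treatment ends for good.

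**Links between the two drugs.** Protocol 6.1.2.1: "If a dose of eribulin is omitted, the corresponding dose/s of balixafortide must also be omitted". The reverse case is not addressed. SAP 9.1.5 records the action taken for each drug. If either drug is withdrawn, "then the AE will be considered as leading to study treatment discontinuation", and the table is also broken down by drug.

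**Analysis rules.** SAP Table 1 censors PFS at the last progression-free scan before another anti-cancer therapy starts. SAP 8.1.2 excludes scans after that start from the response derivation. SAP 8.1.3.1 repeats the PFS analysis without this censoring.

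**The concern.** Eribulin is the approved treatment and balixafortide the addition under test. A patient who cannot tolerate the addition would lose the approved drug as study medication, possibly before its first dose, because of a reaction to the other drug. That is a patient-care question first.

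The analysis is affected second. The investigator may reasonably want to give eribulin anyway. Protocol 5.4.3 restricts anti-cancer drugs only during the treatment phase, so nothing bars it after EoT. It would then be an off-study therapy started before progression. The primary PFS analysis would drop that patient's later follow-up and the ORR analysis would drop the later scans. Control patients never receive balixafortide, so a balixafortide reaction can open this path in one arm only.

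**Working it through.** The plan gives no figure on this point, so the check is mainly a reading of the text.

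**1. Does stopping balixafortide end study eribulin?** Protocol 6.1.2 sends the patient to EoT. Protocol 7.6 describes EoT as the visit for patients who discontinue treatment and equates it with withdrawal. Protocol 5.3.1 defines treatment discontinuation as leaving the treatment phase. SAP 3.4.1 counts the 7 days from the balixafortide stop. Taken together, the patient leaves the treatment phase when balixafortide stops. No sentence says so outright, and none provides for eribulin alone.

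**2. Does any other section supply that provision?**
- Protocol 6.1.2.1 omits balixafortide when eribulin is omitted. It does not say what happens to eribulin when balixafortide is omitted.
- SAP 9.1.5 can record withdrawal of one drug, but counts it as discontinuation of study treatment. It is a reporting rule and grants no permission to continue.
- The permanent stop in protocol 9.2.6.3 could mean balixafortide only. Protocol 6.1.2 then still sends the patient to EoT.

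**3. The Day 1 case.** Most hypersensitivity events occurred at the first administration, which is Cycle 1 Day 1. The first eribulin dose is on Day 2. Followed as written, a severe Day 1 reaction ends treatment with no eribulin given. The per-protocol set in SAP 4.3.5 requires at least one eribulin dose, so the SAP allows for randomized patients who had none.

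**4. If off-study eribulin starts soon after EoT.**
- Treatment starts within 3 days of randomization (protocol 3.3). EoT, with a scan if there is no progression, is within 7 days of stopping and before any new therapy (protocol 7.6).
- The last scan before off-study eribulin is then at most about 3 + 7 = 10 days after randomization. PFS is censored there, or in effect at randomization if that scan was not done.
- A confirmed response needs a second scan at least 4 weeks later, and stable disease needs at least 35 days (SAP 8.1.3). Since 10 is less than 35, the patient is counted as not evaluable unless progression is seen. With measurable disease the patient stays in the ORR denominator (SAP 4.3.6).
- If off-study therapy starts later, the scans before it still count.

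**5. Scale.** No stopping rate appears in the text available (part of the text around protocol 2.5.1 was not). The 3rd line+ population has 320 patients randomized 1:1, so 320 / 2 = 160 per arm. Purely as assumptions, 3%, 5% and 10% would be 0.03 × 160 = 4.8, 0.05 × 160 = 8 and 0.10 × 160 = 16 patients. The higher values sit poorly with the protocol's description of such stops as rare.

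**The case against.** **The text does not order eribulin to stop.** Protocol 6.1.2 only lists visits. Elsewhere the safety visit is timed from the last dose of study drug, and eribulin is study medication in this arm. One could read 6.1.2 as saying that the visits are still owed whenever study drug finally ends. This stands in part: a reader might infer an express instruction to stop eribulin, and there is none. But the deferred reading does not fit SAP 3.4.1, which counts from the balixafortide stop. If sites can read the rule both ways, it needs a sentence in any case.

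**Stopping the whole regimen is defensible.** The trial tests a combination, the doses are called interdependent, and the patient stays in the ITT set and is followed for progression and survival. This is fair. It makes the rule a choice rather than an error, but the documents give no reason for withholding eribulin from someone who reacted to the other drug.

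**Existing handling limits the numbers.** Milder reactions are managed, and stopping is discussed with the sponsor where possible. This stands.

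**Three stronger readings are tempting, and the documents do not support them.**
- *Loss of power.* Any figure would come from an assumed stopping rate, an assumed hazard off drug and an assumed share censored. Nor should the fix be expected to raise power: a patient on eribulin alone, assumed to progress like a control patient, adds such events where censoring would remove them.
- *Bias in a known direction.* The Table 1 rule applies to both arms, and the net effect depends on what these patients receive and when they progress. SAP 8.1.3.1 also provides the uncensored PFS analysis.
- *A one-arm change in scan timing.* The 8-weekly follow-up schedule applies in either arm to anyone off drug without progression. It does not come from this rule.

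**Conclusion.** The point holds as a gap with a real consequence for individual patients. Both documents send a patient who stops balixafortide for toxicity to EoT, neither allows eribulin alone, and a severe Day 1 reaction can mean no study eribulin. If eribulin follows off study before progression, primary PFS loses that follow-up and ORR loses the later scans, by a path that a balixafortide reaction opens only in the combination arm. PFS has an uncensored sensitivity analysis; ORR has no counterpart.

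The size is unknown and probably small. The conclusion rests on the natural reading of protocol 6.1.2 with 5.3.1, 7.6 and SAP 3.4.1, and the analysis consequence also needs off-study therapy before progression. It does not threaten the validity of the trial. It is a cheap improvement that should be made, justified by patient care and a clear rule rather than by power.

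**What to change.** State in protocol 6.1.2 and 9.2.6.3, and repeat in SAP 3.4.1, that when only balixafortide is stopped for toxicity, eribulin continues as assigned study medication, or starts once the reaction has resolved, unless eribulin is itself contraindicated. The patient stays in the treatment phase on its scan schedule, and EoT follows when eribulin stops. Say that this is not cross-over under 6.1.1.

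Add a note to SAP Table 1 and 8.1.2 that eribulin given this way is not new anti-cancer therapy. Eribulin started off study after EoT is handled as already written. The counts in SAP 9.1.5 can stay, with withdrawal of balixafortide alone labelled as such.

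The cost is a short amendment and SAP note, with eribulin supply and visits for a few more patients. There may also be slight dilution of the estimated effect compared with censoring them, because they would contribute follow-up on eribulin alone within the combination arm. No new type of assessment is needed.

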6.1.2.1 Dosing Delays or Interruptions

Patients will start study medication within 3 days from randomization as outlined in the Study Schedule (Section 1.1). Subsequent cycles of treatment should be started within 3 days of completing the previous cycle. Any delays beyond this that are being considered to the beginning of a cycle for logistical or scheduling reasons should be discussed with the Sponsor on a case by case basis.

If study medication during a cycle is delayed for <14 days (counted from the beginning of dosing in that cycle), then treatment can be resumed during that cycle. In these circumstances, the total duration of a cycle could potentially be extended up to 27 days.

Protocol No.: POL6326-009

Version 3.0

If study medication during a cycle is delayed for ≥14 days (counted from the beginning of dosing in that cycle), then treatment for that cycle cannot be resumed. Instead, the next cycle will be initiated as planned. If the next cycle cannot be initiated as planned, the patient should be discontinued from treatment unless discussed and agreed otherwise with the Sponsor.

The doses of balixafortide on Days 1, 2 and 3 are interdependent with the eribulin dose on Day 2. Similarly, the doses of balixafortide on Days 8, 9 and 10 are interdependent with the eribulin dose on Day 9. Therefore, if an eribulin dose is delayed by a few days during a cycle, then the adjunctive balixafortide doses must also be delayed accordingly during that cycle. Although delays of <14 days (counted from the beginning of dosing in that cycle) may change the days on which doses are given in relation to the Schedule, the interval between doses in a cycle should remain the same as those shown in Section 6.1.1. If a dose of eribulin is omitted, the corresponding dose/s of balixafortide must also be omitted. Some examples of the circumstances that could arise are given below:

- Example 1, if eribulin is given on Day 3 instead of Day 2, then balixafortide can be given on Days 2, 3 and 4 instead of on Days 1, 2 and 3.
- Example 2, if eribulin is given on Day 12 instead of Day 9, then balixafortide can be given on Days 11, 12 and 13.
- Example 3, if eribulin is omitted on Day 9, then the balixafortide on Days 8, 9, and 10 can also be omitted.

Tumor assessments must continue to be performed according to the Study Schedule regardless of any dosing delay (Section 8.2).

Recommended Dose Delays for Eribulin

Do not administer eribulin on Day 2 or Day 9, if any of the following occur:

- ANC <1000/mm³.
- Platelets <75000/mm³.
- Common Terminology Criteria for Adverse Events (CTCAE) Grade 3 or 4 nonhematological toxicities.

The Day 9 eribulin dose may be delayed for a maximum of 1 week. If toxicities:

- Do not resolve or improve to CTCAE Grade ≤ 2 severity by Day 16, omit the dose.
- Resolve or improve to CTCAE Grade ≤ 2 severity by Day 16, administer the eribulin at a reduced dose (Table 4) and initiate the next cycle no sooner than 2 weeks later.

Appropriate follow-up assessments should be done until adequate recovery occurs as assessed by the Investigator. This study requires adherence to the ASCO guidelines for minimizing the incidence of febrile neutropenia, including the recommended prophylactic use

Protocol No.: POL6326-009

Version 3.0

of CSFs, where appropriate at the discretion of the Investigator (Appendix 7 ASCO Guidance on the Use of CSFs) (54).

